9.2.2.2 Reporting Procedures for Serious Adverse Events

The investigator is responsible for ensuring that all serious adverse events observed by the investigator or reported by the subject that occur after signing of the informed consent through EOS are recorded in the subject's medical record and are submitted to Amgen. All serious adverse events must be submitted to Amgen within 24 hours following the investigator's knowledge of the event via the applicable eCRF.

9.2.2.3 Reporting Serious Adverse Events After the Protocol-required Reporting Period

There is no requirement to monitor study subjects for serious adverse events following the protocol-required reporting period or after end of study. However, these serious adverse events can be reported to Amgen. In some countries (eg, European Union [EU] member states), investigators are required to report serious adverse events that they become aware of after end of study. If serious adverse events are reported, the investigator is to report them to Amgen within 24 hours following the investigator's knowledge of the event.

Serious adverse events reported outside of the protocol-required reporting period will be captured within the safety database as clinical trial cases for the purposes of expedited reporting.

If the electronic data capture (EDC) system is unavailable to the site staff to report the serious adverse event, the information is to be reported to Amgen via an electronic Serious Adverse Event (eSAE) Contingency Report Form within 24 hours of the investigator's knowledge of the event. See Appendix B for a sample of the Serious Adverse Event Worksheet /electronic Serious Adverse Event Contingency Report Form. For EDC studies where the first notification of a Serious Adverse Event is reported to Amgen via the eSerious Adverse Event Contingency Report Form, the data must be entered into the EDC system when the system is again available.

The investigator must assess whether the serious adverse event is possibly related to any study mandated activity or procedure. This relationship is indicated by a "yes" or "no" response to the question: "Is there a reasonable possibility that the event may have been caused by a study activity/procedure"?

The investigator is expected to follow reported serious adverse events until stabilization or reversibility.

New information relating to a previously reported serious adverse event must be submitted to Amgen. All new information for serious adverse events must be sent to Amgen within 24 hours following knowledge of the new information. The investigator may be asked to provide additional follow up information, which may include a discharge summary or extracts from the medical record. Information provided about the serious adverse event must be consistent with that recorded on the Adverse Event CRF.

If a subject is permanently withdrawn from protocol-required therapies because of a serious adverse event, this information must be submitted to Amgen.

To comply with worldwide reporting regulations for serious adverse events, the treatment assignment of subjects who develop serious, unexpected, and related adverse events may be unblinded by Amgen before submission to regulatory authorities. Investigators will receive notification of related serious adverse events reports sent to regulatory authorities in accordance with local requirements.

Amgen will report serious adverse events and/or suspected unexpected serious adverse reactions as required to regulatory authorities, investigators/institutions, and IRBs/IECs in compliance with all reporting requirements according to local regulations and good clinical practice.

The investigator is to notify the appropriate IRB/IEC of serious adverse events occurring at the site and other adverse event reports received from Amgen, in accordance with local procedures and statutes.

9.2.2.4 Serious Adverse Events That are not to be Reported In an Expedited Manner

Migraine requiring hospitalization does not need to be reported in an expedited manner. AEs, SAEs, safety labs will be reviewed by the GSO, MM, and PI throughout the study and at the DRLM.

9.3 Pregnancy and Lactation Reporting

If a pregnancy occurs in a female subject, or female partner of a male subject, while the subject is taking protocol-required therapies report the pregnancy to Amgen as specified below.

In addition to reporting any pregnancies occurring during the study, investigators should monitor for pregnancies that occur through 12 weeks after the last dose of protocol-required therapies.

The pregnancy should be reported to Amgen's Global Patient Safety within 24 hours of the investigator's knowledge of the event of a pregnancy. Report a pregnancy on the Pregnancy Notification Worksheet (Appendix C).

If a lactation case occurs while the female subject is taking protocol-required therapies report the lactation case to Amgen as specified below.

In addition to reporting a lactation case during the study, investigators should monitor for lactation cases that occur after the last dose of protocol-required therapies through 12 weeks.

Any lactation case should be reported to Amgen's Global Patient Safety within 24 hours of the Investigator's knowledge of event. Report a lactation case on the Lactation Notification Worksheet (Appendix C).

10. STATISTICAL CONSIDERATIONS

- 10.1 Study Endpoints, Analysis Sets, and Covariates
- 10.1.1 Study Endpoints
- 10.1.1.1 Primary Endpoint
 - Occurrence of a migraine-like attack within 24 hours of challenge-agent infusion

10.1.1.2 Secondary Endpoints

- Occurrence of a headache within 24 hours of challenge-agent infusion
- Treatment-emergent adverse events
- Clinical significant changes in vital signs, ECGs, physical examinations, laboratory safety tests and neurological assessments
- AMG 334 PK parameters, including C1 hour and AUC84d
- Anti-AMG 334 antibodies

10.1.1.3 Exploratory Endpoints

- Severity of PACAP-38 induced migraine-like attacks and headaches
- Duration of PACAP-38 induced migraine-like attacks and headaches

- Migraine characteristics: localization, accompanying symptoms and pre-monitory symptoms.
- PACAP-38 related treatment-emergent adverse events
- Evaluate the concentration of PACAP-38 and CGRP following administration of AMG 334

10.1.2 Analysis Sets

10.1.2.1 Safety Analysis Set

The safety analysis set will consist of all subjects who receive investigational product and PACAP-38. Subjects will be analyzed according to the treatment received (AMG334 or Placebo).

10.1.2.2 Pharmacokinetic Concentration Analysis Set

The pharmacokinetic (PK) concentration analysis set will contain all subjects who received investigational product and have at least one PK sample collected.

10.1.3 Covariates and Subgroups

No subgroup analyses are planned.

10.2 Sample Size Considerations

A total of up to 61 migraine subjects are planned to be enrolled into the study. Up to 25 subjects may participate in Part A and up to 36 in Part B of the study. If ambiguous results in Part A occur regarding the ability of PACAP-38 ideally safely triggering a headache in all subjects within a given cohort (although, safely triggering headaches in the majority of subjects within a given cohort may be considered acceptable to advance to Part B of the study) and moderate to severe MLAs in the majority of subjects within the same cohort, then a previously dosed cohort sample size may be expanded to up to 5 subjects per cohort. Once the PACAP-38 dose has been selected, 8 subjects will be randomized to placebo and 8 subjects will be randomized to AMG 334. The data collected for the 16 Randomized (AMG 334 or Placebo) Subjects will be included in the interim analysis (See Section 10.4.1). Following the interim analysis, if the decision is to continue enrollment for the study, an additional 10 subjects will be randomized to AMG 334.

The sample size is based on practical considerations and is consistent with this type of study. If, PACAP-38 produces MLA in 70% of placebo treated subjects, and AMG 334 is effective in blocking MLA such that only 20% of AMG 334 treated subjects have a headache, then there is approximately a 91% chance of overall trial success (Section 10.4.1).

10.3 Access to Individual Subject Treatment Assignments by Amgen or Designees

Blinded individuals will not have access to unblinded information until the study is formally unblinded. Unblinding and potentially unblinding information should not be distributed to the study team, investigators or subjects prior to the study being formally unblinded (eg, the formal unblinding may occur at the final analysis rather than during the primary analysis) except as specified (eg, Section 5.2 and Section 9.2.2.2).

Unless otherwise specified in this section, subjects, site personnel, or Amgen staff and their designees will not have access to unblinding information until the study is formally unblinded. Unblinded individuals, as designated in this section, are to ensure unblinding information and potentially unblinding data are not distributed to blinded individuals until the study is formally unblinded.

A subject's treatment assignment should only be unblinded when knowledge of the treatment is essential for the further management of the subject on this study or may potentially impact the safety of subjects currently enrolled. Unblinding at the study site for any other reason will be considered a protocol deviation. The investigator is strongly encouraged to contact the Amgen clinical study manager before unblinding any subject's treatment assignment, but must do so within 1 working day after the event and must document the unblinding in the subject's eCRF.

Individual subject treatment assignments will be unblinded to personnel from Pharmacokinetics and Drug Metabolism, Clinical Immunology, Biological Sample Management, and Molecular Sciences & Computational Biology departments associated with tracking, assaying, and analyzing the PK samples, biomarker development samples. Furthermore, individual subject treatment assignments will be unblinded to designated personnel from Biostatistics at 2 timepoints during the study: 1) the interim analysis (personnel from Biostatistics performing the interim analysis only), and 2) after formal unblinding (see below). Access to individual subject data will be limited to unblinded staff until the official unblinding occurs. Prior to unblinding, when knowledge of the treatment assignment is essential for the further management of the subject or potentially affects the safety of subjects, the randomization code may be broken.

10.4 Planned Analyses

10.4.1 Interim Analyses

Once 24 hours of data is collected from 16 Randomized (AMG 334 or Placebo) Subjects (8 per group) after PACAP-38 infusion on Day 8, an interim analysis will be performed to

determine if the challenge-agent, PACAP-38, invokes historical rates (~66%) of MLA and if AMG334 has greater efficacy than placebo. If AMG334 is found to block PACAP-38 induced migraines completely, or have the same efficacy as placebo, the study will be terminated. Otherwise, another 20 Randomized (AMG 334 or Placebo) Subjects will be added. Appropriate decision rules, outlined below were developed to determine whether to increase the sample size (up to 10 per treatment) or to stop, either due to demonstration of treatment effect or treatment utility.

Decision rules to be applied during the trial are:

- At the interim analysis, if 3 or less of the 8 placebo subjects have a MLA, the study will be stopped and concluded that PACAP-38 does not induce a sufficient proportion of MLA for the study to test the hypothesis. (TRIAL FAIL (ASSAY)-EARLY)
- At the interim analysis, if 4 or more placebo subjects have a MLA, yet more subjects receiving AMG 334 have them than placebo subjects, then the study will be stopped and concluded that AMG 334 is ineffective in blocking PACAP-38 induced MLA. (TRIAL FAIL--EARLY)
- If the difference at the interim analysis in the proportion of subjects with MLA (placebo-AMG 334) is greater than or equal to 75% then the study will stop early and concluded that AMG 334 is effective in blocking PACAP-38 induced MLA. (TRIAL SUCCESS-EARLY)
- 4. If none of the first 3 decision rules apply at the interim analysis, an additional 20 subjects will be enrolled in the trial. At the end of trial, if the p-value from the one-sided Fishers Exact test is less than 0.1, it will be concluded that AMG 334 is effective in blocking MLA (TRIAL SUCCESS –LATE),, or if the p-value from the one-sided Fishers Exact test is greater than or equal to 0.1, it will be concluded that AMG 334 is ineffective at blocking MLA (TRIAL FAIL –LATE)

The results from 10,000 simulated trials demonstrating the probability of failing at the interim analysis, as well as the probability of overall trial result, for different potential scenarios of the proportion of subjects with MLA in each treatment group are shown below.

Probability of Fail at the Interim Analysis:

Placebo subjects with MLA

20%	35%	50%	70%		
95%	72% 73%	36% 40% 50%	6% 8% 15% 40%	20% 35% 50% 70%	AMG 334 subjects with MLA

Probability of Overall Trial Success:

Placebo subjects with MLA

20	%	35%	50%	70%		
1	%	14% 4%	48% 23% 6%	91% 72% 38% 5%	20% 35% 50% 70%	AMG 334 subjects with MLA

From the above, it can be seen that, if PACAP-38 does not induce a sufficient proportion of MLA for the study to test the hypothesis, or AMG 334 appears to be ineffective in blocking PACAP-38 induced MLA, the trial is more likely to fail at the interim analysis stage (highlighted in bold and underlined in the results with respect to the probability of fail at the interim analysis). However, should the study continue from the interim analysis stage, even by chance, the overall type I error is controlled such that the study is highly unlikely to conclude AMG 334 is effective in blocking PACAP-38 induced MLA (overall trial success) when it is not (highlighted in bold and underlined in the results with respect to the probability of overall trial success).

Designated personnel from Biostatistics will be unblinded for the interim analysis (see Section 10.3). After interim analysis, the designated unblinded Biostatistics personnel will recommend to the study team whether the sample size remains at 8 per group or needs to be increased to 18 per group.

10.4.2 Data Monitoring Committee (DMC), Data Review Team (DRT) or Dose Level Review Team (DLRT)

A Safety Review Meeting or DLRM will be held after PACAP-38 dosing has been completed in each cohort in Part A. Available vital signs and adverse events occurring at least 24 hours following PACAP-38 dosing for each cohort will be reviewed by the PI,

MM, and GSO or designee to decide enrollment in subsequent cohort. If the PI, MM, and GSO or designee decide not to proceed with enrollment in the subsequent cohort, then a Safety Review Meeting or DLRM will be held after the last dosed cohort.

The DLRM members will be composed of the investigator(s), Amgen Medical Monitor, Amgen Global Safety Officer (GSO) or designee, Early Development Leader or designee, Clinical Study Manager or designee, and Biostatistics representative or designee. Additional members may be added as needed (eg, PK Scientist). The Safety Review Meeting Members include the investigator(s), Amgen Medical Monitor, and Amgen GSO or designee. The DLRM and Safety Review Meeting voting members will include the investigator(s), Amgen Medical Monitor, and Amgen GSO or designee.

A DLRM is planned for the Non Randomized (PACAP-38 Only) Dose Selection Subjects only. Unscheduled DLRMs can be called at any time by any of the DLRM voting members.

The Safety Review Meeting and DLRM voting members will decide whether or not to proceed with enrollment in the Randomization (AMG 334 or Placebo) Phase and if the decision is to proceed with enrollment in the Randomization (AMG 334 or Placebo) Phase, the Safety Review Meeting and DLRM voting members will select a PACAP-38 dose. The maximum dose of PACAP-38 will not exceed 115 pmol/kg. At any time the PI, MM, and GSO or designee may decide to add additional Non Randomized (PACAP-38 Only) Dose Selection Subjects pending review of emerging safety, and/or tolerability data. A future modification of the PACAP-38 dose may occur based on emerging safety, and/or tolerability findings.

All available study data, including the headache questionnaires, demographics, investigational product administration, medical history, concomitant medications, adverse events (including MLA), ECGs, vital signs, and laboratory results will be reviewed. Data to be reviewed at the Safety Review Meeting and DLRMs during the PACAP-38 Dose Selection Phase will not be blinded. Data to be reviewed for any unscheduled DLRM post the PACAP-38 Dose Selection Phase will be revealed) unless unblinding is deemed necessary for the review team to make dosing decisions. If deemed necessary, unblinding will be performed to assist dose decisions in accordance with Amgen standard procedures.

10.4.3 Primary Analysis

The primary analysis will take place after all subjects have completed the study.

10.4.4 Final Analysis

The final analysis will take place after final database lock.

10.5 Planned Methods of Analysis

10.5.1 General Considerations

Descriptive statistics will be provided for selected demographic, safety and PK data. Descriptive statistics on continuous measurements will include means, medians, standard deviations, and ranges, while categorical data will be summarized using frequency counts and percentages. Comparison of PACAP-38 ability to produce MLA between AMG 344 and placebo will be done with Fisher's Exact Test. Unless otherwise specified, data will be summarized using the safety analysis set, by actual treatment group. If a subject receives IP, but does not receive PACAP-38, their data will be listed only; their data will not be included in any summaries or analyses.

10.5.2 Primary Endpoint

The number and percent of subjects experiencing a MLA within 24 hours after PACAP-38 infusion will be summarized for each treatment group. Comparison of PACAP-38 ability to produce MLA between AMG 334 and placebo will be done using the Fisher's Exact test.

10.5.3 Secondary Endpoints

10.5.3.1 Number of Headaches

The number and percent of subjects experiencing a headache within 24 hours after PACAP-38 infusion will be summarized for each treatment group. Comparison of PACAP-38 ability to produce headaches between AMG 334 and placebo will be done using the Fisher's Exact test.

10.5.3.2 Safety Endpoints

Subject incidence of adverse events will be summarized by system organ class and preferred term for all treatment-emergent, serious treatment emergent, IP related, those leading to withdrawal of investigational product, fatal, and of special interest (if applicable). The identification of adverse events of special interest is a continuous process. Events may be identified and documented as the safety profile of the drug is characterized.

Vital signs will be listed and reviewed for each subject. Depending on the size and scope of change in vital signs, summaries may be provided.

For ECGs measurements following PACAP-38, summaries over time and/or changes from baseline over time will be provided for all ECG parameters. Baseline will be defined measurements taken on Day 8 Pre-Dose. A subject's maximum change from baseline in QTcF and QTcB will be categorized and the number and percentage of subjects in each treatment group will be summarized. A subject's maximum post baseline values will also be categorized and the number and percentage of subjects in each treatment group will be summarized.

Hematology, biochemistry, and urinalysis data will be listed and reviewed for each subject. Values outside the normal laboratory reference range will be flagged as high or low on the listings. Depending on the size and scope of changes in laboratory data, summaries of laboratory data over time and/or changes from baseline over time may be provided.

Subject incidence of treatment-emergent suicidal ideation and behaviour as assessed by C-SSRS will be listed.

Binding antibody and neutralizing antibody formation will be assessed at predose and at various time points throughout the study including EOS. Antibody data will be listed for each subject. The incidence and percentage of subjects who develop anti-AMG 334 antibodies (binding and if positive, neutralizing) at any time may be tabulated.

10.5.3.3 Pharmacokinetic Endpoints

Serum AMG 334 concentrations will be determined using a validated assay. Individual serum concentration-time plots for AMG 334 will be presented for each subject as well as mean concentration-time plots for each treatment group. PK parameters $C_{1 hour}$, and AUC_{84d} will be estimated using either compartmental (eg, PK modeling) or non-compartmental methods. Actual dosing and sampling times will be used for calculation of PK parameters. Summary statistics will be generated for each PK parameter for each treatment group. The PK concentration analysis set will be used for these analyses.

10.5.4 Exploratory Endpoints

10.5.4.1 Migraine-like Attacks (MLA) and Headaches

The reduction in severity by AMG 334 of MLA and headaches within 24 hours after infusion of PACAP-38 will be assessed and summarised based on a severity score (0-10; 0=pain free; 10=extreme pain). For MLA and headaches separately severity scores will be analysed using a repeated measure analysis of variance model.

Independent variables will be treatment, hour and treatment by hour interaction. Subject will serve as a random effect. For each treatment by hour combination, least square means, ratio to Placebo, 95% confidence intervals and p values for the null hypothesis of no difference from placebo will be presented. Graphical summaries of severity scores will also be provided. In addition, descriptive statistics will be provided for the duration of MLA and headaches.

Descriptive summaries of measured characteristics of MLA and headaches, such as localization and accompanying symptoms and pre-monitory symptoms, within 24 hours after infusion with PACAP-38 will be presented for each treatment group.

10.5.4.2 PACAP-38 Related Treatment Emergent AEs

Subject incidence of PACAP-38 related treatment emergent AEs will be summarized by system organ class and preferred term.

10.5.4.3 Plasma PACAP-38

Summary statistics will be generated for plasma PACAP-38 levels pre/post dosing with AMG 334 and PACAP-38.

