A single dose of 140 mg of AMG 334 or matching placebo will be administered intravenously on Day 1. The quantity, volume, start date/time, stop date/time, and blinded investigational product concentration will be recorded on the individual subject's Blinded Investigator Product Administration eCRF prior to initial database lock. Following initial database lock, upon written authorization from Amgen, the package lot number and unblinded dose of the investigational product will be recorded on each subject's Investigational Product Administration eCRF.

Time (day)

The effects of overdose of AMG 334 are not known. Overdose with this product has not been reported. All overdose occurrences must be documented and corresponding adverse events must be recorded on the appropriate eCRF and in the source documents.

The dosing schedule is described by a schema in the protocol synopsis.

6.2.1.2 Dosage Adjustments, Delays, Rules for Withholding or Restarting, Permanent Discontinuation for AMG 334

Further dosing of AMG 334 will be stopped or modified to a lower dose if suspected adverse drug reactions and/or changes in safety data (including but not limited to vital signs, ECG, or clinical laboratory results) are observed and these changes pose a health risk.

Clinically or medically significant suspected adverse drug reactions, and serious adverse events considered to be related to study procedures will be followed until resolved or considered stable. The study may be terminated at any point in time at the discretion of the sponsor.

The dosing schedule is described by a schema in the protocol synopsis.

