Drug, Alcohol & Cotinine Screen	Х	Xj					X ^{h j}													
HIV, HepCAb, HBsAg, HBcAb	Х																			
Postmenopausal status test, (females only) ^k	Х																			
Cardiac Enzymes	Х	Х					Х					Х		Х	Х	Х				
Pregnancy Test (females only) ^d	Х	Х					Х													Х
Questionnaires																				
Headache Questionnaire		Х						Х	Х	Х	Х	Х	Х	Х	Х	Х				
Columbia-Suicide Severity Rating Scale	Х	Х	х				х									Х		Х	Х	Х

Table 2. Schedule of Assessments For Part B: Randomized (AMG 334 or Placebo) Subjects

Footnotes are defined on the next page of table

Page 1 of 2

Activity	Screeni	Treatment Period											Fo	EOS Visit						
Study Day	-21 to -2	-1		Day 1 ^ª				Day 8 ^{b f g}										Day 29	Day 57	85
Time (in hours)			Pre- Dose	0	0.5	1	Pre- Dose	0	0.25	0.5	1	2	3	4	8	24	48			
Dosing																				
Study Drug Administration				Х																
Challenge-agent (PACAP-38) ^f								X ^f												
Pharmacokinetic and Other Blood	Samples																			
Antibody Sample Collection			Х															Х	Х	Х
AMG 334 Serum PK Collection ^e			Х			Х	Х			X e								Х	Х	Х
CGRP Plasma Collection			Х				Х		Х	Х										Х
PACAP-38 Plasma Collection							Х		Х	Х										
Cell Pellet for Pharmacogenetics			Х																	

Table 2. Schedule of Assessments For Part B: Randomized (AMG 334 or Placebo) Subjects

Page 2 of 2

Abbreviations: ECG = electrocardiogram; EOS = end of study; FSH = follicle-stimulating hormone; HepBsAg = hepatitis B surface antigen; HepCAb = hepatitis C antibody; HBcAB = hepatitis B core antibody; HIV = human immunodeficiency virus; PK = pharmacokinetic

^{a.} Subjects will return to the research facility one day prior to investigational product administration (Day -1), at which time baseline procedures will be completed. After completion of all pre-dose and baseline laboratory and vital sign procedures on the day of dosing (Day 1), subjects will receive AMG 334 or matching placebo. -Subjects will reside at the research facility for at least 1 hour and then be discharged home.

^{b.} Subjects will return to the research facility on Day 8, at which time pre-dose procedures will be completed. After completion of pre-dose procedures on Day 8, subjects will receive PACAP-38. Subjects will reside at the research facility for at least 24 hours post PACAP-38 infusion and then be discharged home.

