7.2.26 Blood Sample Collection for PACAP-38 Concentrations

Blood samples for PACAP-38 plasma concentrations will be collected for all subjects at time points specified in the Schedule of Assessments (Table 2 and Table 3). Detailed

instructions on sample collection, processing, and shipping will be provided in a separate manual.

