10.5.4.4 Plasma CGRP

Summary statistics will be generated for plasma CGRP levels pre/post dosing with AMG 334 and PACAP-38.

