10.11 Exposure to Concomitant Medication

All medication will be coded using the World Health Organization Drug (WHO DRUG) dictionary. All prior and concomitant medications will be reviewed.

11. Changes From Protocol-specified Analyses

Minor changes to the protocol-specified analyses have been made and clarified in this SAP.

The safety analysis set has been modified slightly to include all subjects who receive IP (AMG 334 or placebo), but excludes any reference to whether the subject receives PACAP-38 or not. This is to take into account any subjects that receive IP, but do not receive PACAP-38 (eg, subject withdrew from the study before PACAP-38 could be administered). In these cases, the subject's data will be reviewed, but will not be included in any data summaries.

ECG data will not be summarized as specified in the protocol, as the data was collected as part of the standard of care and not in a thorough manner.

12. Literature Citations / References

Headache Classification Subcommittee of the International Headache Society. The international classification of headache disorders, 2nd edition. *Cephalalgia*. 2004; 24(Suppl. 1):8-160.

13. Data Not Covered by This Plan

The following analyses will be analyzed outside of this SAP:

- The changes in plasma PACAP-38 and CGRP concentrations pre- and post-dosing with AMG 334
- Blood samples collected for biomarker development

Statistical Analysis Plan: 20140207 Date: 17 May 2017 Page 27

14. **Appendices**

Statistical Analysis Plan: 20140207

Date: 17 May 2017 Page 28

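### In the Amendment 3 protocol, the planned pre/post AMG 334 summary of plasma PACAP-38 has no dedicated sample taken before AMG 334

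*Protocol*

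**What the plan says.** Protocol section 10.5.4.3 plans the following: "Summary statistics will be generated for plasma PACAP-38 levels pre/post dosing with AMG 334 and PACAP-38". Section 10.5.4.4 says the same of the other peptide: "Summary statistics will be generated for plasma CGRP levels pre/post dosing with AMG 334 and PACAP-38". Both serve one exploratory endpoint in section 10.1.1.3: "Evaluate the concentration of PACAP-38 and CGRP following administration of AMG 334".

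On timing, section 6.2.1.1 says: "A single dose of 140 mg of AMG 334 or matching placebo will be administered intravenously on Day 1". Section 7.2.26 sets no time points of its own for PACAP-38: "Blood samples for PACAP-38 plasma concentrations will be collected for all subjects at time points specified in the Schedule of Assessments". In Table 2 (section 7.1), the Part B schedule, the row "PACAP-38 Plasma Collection" is marked on Day 8 only. The row "CGRP Plasma Collection" is also marked at Day 1 pre-dose.

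The SAP follows Amendment 4 (21 Oct 2016), not the supplied Amendment 3. Its section 10.7.4 summarises both peptides before and after PACAP-38, with summaries by treatment group for the second PACAP-38 dose. Its section 13 lists, among analyses to be done outside the SAP: "The changes in plasma PACAP-38 and CGRP concentrations pre- and post-dosing with AMG 334".

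**The concern.** Two analytes share one analysis sentence but not one sampling schedule. For CGRP, a value before AMG 334 can be set against later values. For PACAP-38, the first scheduled sample comes a week after AMG 334. The CGRP row suggests that this is an oversight, since nothing in the protocol explains why only one of the two peptides has a baseline draw.

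What is at stake is one exploratory description: whether circulating PACAP-38 in a subject differs before and after CGRP-receptor blockade. With 8 to 18 subjects per arm, each subject's own baseline would help in reading that description.

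**Working it through.** The plan gives no figure to reproduce here. The check sets the schedule against the analysis sentence.

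**Step 1: read the columns.** Each mark in Table 2 was matched to its column. Rows with known timing confirm the alignment: study drug falls at Day 1 hour 0, the PACAP-38 challenge at Day 8 hour 0, and antibody samples at Day 1 pre-dose and Days 29, 57 and 85.

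**Step 2: place the samples around AMG 334 (Day 1, hour 0).**

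| Plasma analyte, Part B | Before AMG 334 | After AMG 334 | Count |
|---|---|---|---|
| CGRP | Day 1 pre-dose | Day 8 pre-dose, 0.25 h, 0.5 h; Day 85 | 1 before, 4 after |
| PACAP-38 | none | Day 8 pre-dose, 0.25 h, 0.5 h | 0 before, 3 after |

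On Day 8, pre-dose means before PACAP-38. It is nominally 8 − 1 = 7 days after AMG 334.

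**Step 3: see which PACAP-38 summaries the samples support.**

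- Before and after PACAP-38, by treatment group: yes (Day 8 pre-dose against 0.25 h and 0.5 h).
- AMG 334 against placebo before the challenge: yes (Day 8 pre-dose, between arms).
- Before and after AMG 334, within subject or as group summaries: not from the scheduled PACAP-38 samples, because there is no earlier value.

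**Step 4: look for a pre-AMG 334 value elsewhere in Amendment 3.** Section 7.2.26 only points back to the schedule. Table 2 has no PACAP-38 plasma at screening or Day -1. Table 3 (Part A) does take PACAP-38 plasma at pre-dose, 0.25 h and 0.5 h. However, exclusion 4.2.17 bars anyone who has already entered the study or received PACAP-38, so under Amendment 3 those samples belong to different people.

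**Step 5: compare with the SAP's design.** SAP section 3.1 randomises only subjects who have already responded to PACAP-38, either in Part A or in a challenge period before AMG 334. Part A responders may therefore have Table 3 samples that precede AMG 334. For PACAP-38-naïve subjects, sampling at the first challenge would be set by the Amendment 4 schedule, which is not supplied. Step 4's conclusion therefore cannot be carried over to Amendment 4.

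**The case against.** The strongest case against the point is that it concerns a superseded schedule. A reader might infer from SAP section 13, which still lists the pre/post AMG 334 change, that the trial as run lacked the baseline. The documents do not support that. The SAP's expectation rests on Amendment 4, where every randomised subject receives PACAP-38 before AMG 334 or placebo. SAP section 10.7.4 singles out the second PACAP-38 dose for its by-treatment summaries, which is consistent with first-dose samples existing but does not prove it. This objection stands and limits the point to Amendment 3.

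A reader might also infer that the summary is impossible under Amendment 3. That is too strong. Sections 7.2 and 7.6 allow any scheduled blood sample to be used for any test in the protocol, so the Day 1 CGRP plasma could in principle be assayed for PACAP-38. No such use is planned, and whether the tube and handling would suit depends on separate manuals. What can be said is that no dedicated sample is scheduled.

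Third, the endpoint in section 10.1.1.3 asks only about concentrations after AMG 334, and Day 8 samples provide those. In a randomised comparison, the Day 8 pre-dose difference between arms estimates the AMG 334 effect without a baseline. This is correct, but it leaves the sentence in section 10.5.4.3 unmet. One could read that sentence as covering only the Day 8 samples. SAP section 13, which names pre- and post-dosing with AMG 334 as an analysis of its own, supports the plainer reading.

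Finally, a reader might tie the gap to the trial's main question. Section 2.5 asks whether CGRP lies downstream of PACAP-38. An effect of CGRP-receptor blockade on endogenous PACAP-38 is the reverse direction, which section 2.5 does not pose.

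**Conclusion.** The point holds for the supplied protocol, as a mismatch between one analysis sentence and one row of Table 2. If sampling follows Table 2 and stored CGRP plasma is not re-used, all 16 to 36 randomised subjects lack a pre-AMG 334 PACAP-38 value, while CGRP has one scheduled for everyone. Whether the mismatch survives in Amendment 4 is unknown.

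The consequence is small. The summary is exploratory and descriptive. The pre/post PACAP-38 summary and the between-arm comparison at Day 8 pre-dose remain available. The Fisher's exact test on migraine-like attacks, its decision rules and the safety analyses do not use these samples.

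**What to change.** In order of preference:

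1. Add a PACAP-38 plasma aliquot to the Day 1 pre-dose draw in Table 2, where CGRP, AMG 334 serum, antibody and cell-pellet samples are already taken. The cost is one tube and one assay per randomised subject, 16 to 36 of each, with no new visit or venepuncture.
2. If the Amendment 4 schedule already has a PACAP-38 sample taken before both AMG 334 and the first PACAP-38 challenge, name that visit as the baseline. This costs one sentence. Naming it matters because SAP section 6 takes the last assessment before investigational product as the default baseline. If Amendment 4 samples the first challenge as Table 3 does (an assumption), that default could select a post-challenge value.
3. If neither is possible, restate the PACAP-38 part of protocol section 10.5.4.3 and SAP section 13 as pre/post PACAP-38 by treatment group, as SAP section 10.7.4 already has it, plus AMG 334 against placebo at Day 8 pre-dose. This is a text change only, and it gives up the within-subject view of AMG 334. The CGRP wording can stay.
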